Aim 2a: Evaluate uptake, usage, and views of a home testing nudge platform (encouraging home testing, protective health behaviors, and targeted behavioral nudges delivered via text messages) in a community-based, adaptive intervention trial (N=600) targeting individuals affected by diabetes through collaborations with community partner sites (faith- and community-based organizations, Grady Diabetes Clinic, and COVID-19 community testing and vaccine distribution sites).

Aim 2b: Evaluate changes in vaccine uptake and hesitancy among study participants and family members after implementation of the home-based testing nudge platform.

3. Background

This study leverages data collected during Project PEACH 1 (Promoting Engagement and COVID-19 Testing for Health), a RADx-UP funded study to understand barriers to effective and equitable COVID-19 testing in high-risk and minority populations in Georgia that are affected by diabetes. PEACH 1 applied mixed-methods (quantitative, qualitative, geographic and spatial analysis) to gather evidence to describe COVID-19 epidemiology, locate regions and populations with low testing and vaccine uptake, and targeting key informant interviewing and monitoring social and news media, to identify barriers, motivators, and perceptions around COVID-19 as well as related behaviors among different populations and regions.

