Home-based testing may help people overcome barriers to testing (identifying where to get tested, scheduling and attending appointments, stigma).⁹ However, in order for it to be successful we need to understand the feasibility, acceptability, and sustainability of at-home testing as well as the perceived advantages and disadvantages of home-based testing compared to clinic-based testing among the high-risk population of individuals affected by or at risk for diabetes. This information can be used to create targeted behavioral “nudges”.¹⁰ Nudges are indirect suggestions and positive reinforcements designed to encourage certain choices. They may be a useful means of promoting acceptability and usage of home-based testing as well as increasing an understanding of and acceptability of other key preventive behaviors like COVID-19 vaccination. These targeted messages, sent via text messages, would be designed based on findings from PEACH 1 and the Georgia CEAL Study (1OT2HL156812-01/16-312-0217571-66105L). Behavioral nudges have been shown to have a noticeable effect on health behaviors and study recruitment,^{11,12} however, research testing the application of behavioral nudges relating to behavior change around disease prevention in a pandemic situation is needed.

4. Study Endpoints

Aim 1 Endpoint: Development of a suite of behavioral nudges text message designed to inform (Knowledge) and encourage (Persuade) study participants to perform COVID-19 testing at home or at other locations (primary behavior change focus) and other COVID-19 prevention activities (masking when needed, vaccination/boosters, etc.). Persuasive messaging will address perceived characteristics of COVID-19 testing and home-based testing (relative advantage, compatibility, complexity, trialability, observability) and be adapted to subgroups such as vaccination status and demographic data provided in the baseline survey.

Aim 2a Endpoint: Evaluation of uptake, usage, and perception of a community-based, adaptive intervention trial targeting individuals affected by diabetes through collaborations with community partner sites. The intervention entails reporting of COVID-19 testing via a text-based reporting system and targeted behavioral nudges delivered via text messages.

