Aim 2b: Evaluation of changes in vaccine uptake and hesitancy among study participants and family members post-implementation of the home-based testing platform as well as acceptability of nudges to affect behavior change.

5. Study Intervention/Design

PEACH² is a community-based, mixed methods, randomized, adaptive intervention trial, targeting individuals affected by diabetes. Study participants will be randomized into the PEACH² Intervention Arm or the Control Arm (*See Figure 1 below*). Participants may also opt to participate in an in-depth interview at the end of the intervention and/or to contribute social media data (see descriptions below).

All participants will be asked to complete surveys at baseline and again post intervention at Months 4 and end of follow-up at month 12. The intervention period will last 16 weeks. Baseline surveys will capture demographic data, history of COVID-19, diabetes and diabetes risk factors, views about COVID-19 risk factors and preventive behaviors, and experiences with COVID-19 testing; follow-up surveys at 4 and 12 months will collect information on intervention acceptability, COVID-19 testing, prevention, and vaccine behaviors and views from all participants.

[figure not shown]
PEACH² Intervention Participants: Intervention arm and control arm participants will be sent weekly text messages throughout the intervention period. Control arm participants will receive messages with general diabetes prevention/management information including messages on COVID-19 prevention, but these messages will not be tailored to the participant.

Intervention arm participants will receive weekly text messages with behavioral nudges targeted to their demographic and vaccination group targeting COVID-19 prevention behaviors. Results of qualitative interviews, social media reporting, and feedback from community partners from Project PEACH will be analyzed and used to draft group specific nudges for testing and other prevention behaviors. In weeks 4, 8, and 12, participants will be sent a series of text messages to determine if:

1. They had any COVID-19 symptoms in the past 4 weeks; and, if so:
2. They did a COVID test.

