Results of the nudging trial will be shared with collaborating partners through in-person meetings, feedback sessions and presentations, and with participants through an end-of-study newsletter.

9. Study Timelines

The duration of time an individual will be asked to participate in the study will be approximately 12 months, from completion of baseline survey through enrollment and randomization, participation in the nudge intervention trial and follow-up surveys and interviews.

10. Inclusion and Exclusion Criteria

Inclusion criteria: English speaking adults, at or over the age of 18, living in Georgia, with access to a cellphone, not currently pregnant, and at-risk for diabetes, have diabetes, or are a family caregiver of someone living with diabetes. Participants must agree to receive text messages and be randomized to the intervention or control arm of the study.

Exclusion Criteria: Individuals that do not meet the inclusion criteria or are unwilling to receive text messages or be randomized will not be eligible.

11. Population

The study population for Project PEACH² will be recruited in both urban and rural areas of Georgia to capture inherent diversity in geographic and population characteristic backgrounds which may affect differences in response to COVID-19 risk, attitude, barriers, and testing strategies in the area.

12. Vulnerable Populations

Participants must be able to use a cellphone to receive nudge messages. Therefore, prisoners, adults unable to consent, and children under the age of 18 will not be included in the study. Pregnant women with or at risk for diabetes need different and specific advice and therefore would require specific health messaging that is targeted to pregnant women, and is out of the scope of this study. Pregnant women will not be included.

13. Local Number of Participants

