Six hundred (n=600) participants will be recruited to participate in the study, and randomly assigned to participate in the intervention and control groups. Randomization will be done using a random allocation table created in SAS. Study participants that indicate they would be willing to participate in an interview will comprise the qualitative interview sampling frame. From total study sample, up to thirty in-depth interviews will be conducted with information rich individuals from the Control (N=10) and PEACH² Intervention (N=30) arms. Interview participants will be purposively selected based on data collected in the baseline survey. Demographics, vaccination status, prior experience with COVID-19 and testing, and testing reporting will be considered when compiling the contact list for interview.

The sample size of 600 was estimated using the following assumptions: (a) 80% power; (b) Alpha of 0.05; and (c) the percentage of participants receiving a COVID-19 test in the past month in the control arm would be equal to the percentage of the Georgia population getting a PCR test for COVID-19 in the month of June: 3.44 (standard deviation [SD] 0.49). Using these assumptions, a sample size of 520 (260 per study arm) will be powered to see a 4.5% increase in the percentage of individuals receiving COVID-19 test in the intervention arm compared to controls. We plan to randomize 600 individuals to allow for attrition.

Social media analysis enrollment

Given the complexity of the data download and upload process for participants to complete, we anticipate a significant amount of attrition. Thus, we will conduct individual phone call follow-ups with a selected subset of participants who had consented to being contacted about sharing their social media data for the study, but have not at that time completed the social media data contribution process. As we are conducting this data collection as a proof-of-concept, participants chosen for individual follow-up would be sampled (out of those who indicated use of a social media platform of interest) to cover different demographic groups and other characteristics that are represented by the broader participant pool, and from both the control and intervention arms. We aim to conduct individual follow-up with up to 50 participants.

14. Recruitment Methods

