Participant survey data will be exported by a member of the study team with access to REDCap and uploaded via HTTPS via 2-Factor VPN to one of two databases which support the Dashboard and the Nudge Platform. This export will include a “participantId”, which is a pseudo ID unique to this study and has no relationship to other participant identifiers.

The Limited Study Database (DB) will be maintained separately from both the social media data collection and analytics platform, and from the Nudge Database (DB) to minimize risks and control access. The Limited Study DB used by the Dashboard will contain the participantId, age in years, race, ethnicity, gender, testing history, vaccine status, diabetes status, study enrollment status and history; if provided, participant social media account and activity data will be maintained in the Limited Study Database following collection and anonymization. The Nudge DB will contain the participantId, cell phone number, first name, nudge response, nudge status, and an optional REDCap survey link.

The Nudge Platform will only be accessible via the Dashboard. The Dashboard will implement role-based access controls to limit who is able to send nudge messages to approved study staff. Operators of the Dashboard will have access to nudge responses and the status of a nudge message, but no operator will have direct access to the participant phone numbers, first name, or personalized survey link (if used). Nudges will be delivered to users via the Twilio SMS text messaging platform using secure communications. Nudge responses will be delivered via secure callbacks to the Nudge Platform via Twilio.

Should the study include social media data collection from participants, this will be collected via a secure website using a non-reversible encrypted user key which can only be mapped to the participantId (or other information) in the Limited Study DB. Both the Nudge Dashboard and Platform will be developed and maintained by the Georgia Tech study team. Access will be restricted to select members of the study team. All access to the Dashboard by EU, MSM or GT will require a Georgia Tech account or guest account, sponsored by the GT sub-award Co-PI. Access will require the use of 2-Factor authentication to a VPN and 2-Factor authentication to the web Dashboard. No public access will be possible. The Nudge Platform will only support access via the Dashboard. Certificate-based authentication for all transactions with the Nudge

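### The stated 80% power for a 4.5% increase is wrong as written: on the plan's own figures 260 per arm gives about 60% two-sided, or 72% one-sided

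*Combined protocol and SAP*

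**What the plan says.** The sample-size statement appears twice, in Section 13 (Local Number of Participants) and Section 25 (Resources Available). Both give 80% power and alpha 0.05. The control-arm percentage tested in the past month "would be equal to the percentage of the Georgia population getting a PCR test for COVID-19 in the month of June: 3.44", with an SD of 0.49 attached and no year for the June. The conclusion is that "a sample size of 520 (260 per study arm) will be powered to see a 4.5% increase" in the intervention arm over control, and 600 are randomized to allow for attrition. The test, its sidedness, and whether 4.5% is absolute or relative are not stated.

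Section 25 adds a two-stage recalculation of sample size from first-stage data, because the status of COVID testing is changing quickly. It gives no rule. Section 26 gives the study total as 600.

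On what is being promoted and measured, Aim 2a is to "Evaluate uptake, usage, and views of a home testing nudge platform (encouraging home testing, protective health behaviors" and more, and Section 4 describes messages that encourage "study participants to perform COVID-19 testing at home or at other locations (primary behavior change focus". Section 5 says that "follow-up surveys at 4 and 12 months will collect information on intervention acceptability, COVID-19 testing, prevention, and vaccine behaviors and views from all participants".

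**The concern.** This is the only effect size in the plan and the only justification for 520 analysed and 600 randomized. When two percentages near 3% and 8% are compared, the variance in the higher arm is more than double that in the lower arm, and 260 per arm looks too few for 80% power at a 4.5-point difference.

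If the statement is wrong, the damage falls on interpretation. A null result on testing could be reported as having had an 80% chance of finding a 4.5-point effect when the chance was nearer 60%. The planned recalculation would also start from an incorrect baseline.

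A second, lesser question is whether 3.44% is a suitable control rate. It counts PCR tests in the general population of Georgia, whereas the trial's outcome is any COVID-19 test, and home tests are central to the intervention.

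**Working it through.** **Inputs (Sections 13 and 25).** Control rate p1 = 0.0344; increase d = 0.045, read first as percentage points, so p2 = 0.0794; n = 260 per arm; alpha 0.05; target power 80%. Sidedness is not stated, so both are shown. Normal quantiles: 1.960 (two-sided) or 1.645 (one-sided), and 0.8416 for 80% power.

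**Step 1: try to reproduce 260 per arm.** Variances: p1(1 − p1) = 0.0344 × 0.9656 = 0.0332; p2(1 − p2) = 0.0794 × 0.9206 = 0.0731; sum 0.1063.

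Unpooled formula, two-sided: n = (1.960 + 0.8416)² × 0.1063 / 0.045² = 7.849 × 0.1063 / 0.002025 ≈ 412.

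| n per arm for 80% power | Two-sided | One-sided |
|---|---|---|
| Pooled variance under the null | 415 | 327 |
| Unpooled | 412 | 325 |
| Arcsine | 400 | 315 |
| Continuity-corrected | 459 | 370 |

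None returns 260. One shortcut comes close, which is to use the control variance in both arms: 7.849 × 2 × 0.0332 / 0.002025 ≈ 257.5, or 258 per arm. This may be where the figure came from. It ignores the larger variance at 7.94%, so it does not support 80% power.

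**Step 2: power at 260 per arm.** Pooled rate = (0.0344 + 0.0794)/2 = 0.0569. Standard error under the null = √(2 × 0.0569 × 0.9431 / 260) = 0.02032. Standard error under the alternative = √(0.1063 / 260) = 0.02022.

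- Two-sided: (0.045 − 1.960 × 0.02032)/0.02022 = 0.256, power 60.1%.
- One-sided: (0.045 − 1.645 × 0.02032)/0.02022 = 0.573, power 71.7%.

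Enumerating the chi-square test gives 61.0% and 73.0%; Fisher's exact test gives 54.5% and 67.0%.

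**Step 3: what 80% would need.** 415 per arm (830 analysed) two-sided or 327 per arm (654) one-sided, both above 600. With all 600 analysed and no attrition, power is 66.3% or 77.0%. With 260 per arm, the difference detectable at 80% power is 6.0 points (two-sided) or 5.2 points (one-sided).

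**Step 4: other readings of 4.5%, two-sided, 260 per arm.**

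- Relative: 3.44 × 1.045 = 3.59%; power 3.1%.
- A rise to 4.5%: power 9.0%.
- A comparison of means with SD 0.49 and a relative change of 0.045 × 3.44 = 0.155: 158 per arm. This does not suit a yes/no outcome and does not reproduce 260.

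**Step 5: sensitivity to the control rate.** If the SD of 0.49 is in percentage points, rates within two SD (2.46% to 4.42%) give power for +4.5 points of 68% to 54% two-sided and 78% to 66% one-sided. Power of 80% is reached only if the control rate is about 1.2% (two-sided) or 2.2% (one-sided).

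In the table below, every control rate other than 3.44% is assumed. The last column instead holds the odds ratio implied by the plan, (0.0794/0.9206)/(0.0344/0.9656) = 2.42.

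| Control rate | Detectable difference at 80%, points (two-sided / one-sided) | Power for +4.5 points (two-sided) | Power at odds ratio 2.42 (two-sided) |
|---|---|---|---|
| 1% | 4.3 / 3.6 | 83% | 23% |
| 3.44% (plan) | 6.0 / 5.2 | 60% | 60% |
| 5% | 6.8 / 5.9 | 51% | 75% |
| 10% | 8.6 / 7.5 | 35% | 94% |
| 30% | 11.8 / 10.4 | 19% | above 99% |

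A higher true rate lowers power if the effect is fixed in points and raises it if the effect is fixed as an odds ratio.

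**The case against.** The strongest reply is that the plan names neither the test nor the scale, so the 60% depends on a reading the text does not fix. That is fair as a caveat, but it does not rescue the claim. The percentage-point reading is the most favourable of the three readings on proportions, and the means comparison does not fit the outcome.

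A second reply is that the recalculation in Section 25 deals with uncertainty about the inputs. It could change the final number, but it has no stated rule and does not make the printed 80% correct.

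Third, the consequence is limited. The primary objective is feasibility, acceptability and sustainability, and testing of the nudges is secondary. Section 14 shows that data collection had already begun. This stands, and it is why the remedy is a restatement.

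Two stronger inferences go beyond the documents. A reader might conclude that the PCR figure makes the trial underpowered. The plan presents it openly as an assumption, gives no any-test rate to compare it with, and the direction of the effect cannot be determined. A reader might also conclude that the text-message items cannot yield an any-test rate, because Section 5 asks first whether "They had any COVID-19 symptoms in the past 4 weeks; and, if so", and only then about a test. Section 24, however, describes a symptom answer and a test answer with no such condition. The sections need reconciling; neither settles the matter alone.

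**Conclusion.** Wrong as written. Under an absolute reading, a two-proportion test, equal allocation and 520 analysed, the plan has about 60% power two-sided or 72% one-sided for 4.5 points over 3.44%, not 80%. No standard two-proportion variant checked recovers either 260 per arm or 80% power, and no control rate within two SD of 3.44% does so at 4.5 points, if the SD is in percentage points.

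The mismatch between a PCR population rate and an any-test outcome is real but secondary, since its effect on power is unknown. Nor do the documents support a demand that enrolment rise, that the recalculation follow a particular blinding rule, or that 600 be treated as a cap. The recalculation lacks operational detail, which is a separate matter from the arithmetic error.

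**What to change.** In Sections 13 and 25, state the test, the sidedness and that 4.5% is an absolute difference. Then restate the figure for 520 analysed without changing enrolment: about 60% power for 4.5 points, or 80% power for about 6.0 points, if two-sided; 72% and 5.2 points if one-sided.

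As a secondary note, say that 3.44% is a population PCR rate for an undated June, and do one of two things. Either tabulate the detectable difference over control rates labelled as assumed, or use the arm-pooled past-month testing rate from the baseline survey, if it has such an item. Section 9 describes participation as running "from completion of baseline survey through enrollment and randomization", which places that survey before randomization. The Section 18 data list ("age in years, race, ethnicity, gender, testing history, vaccine status, diabetes status") shows that testing history is held but not that a past-month item exists.

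Before text responses feed the Section 25 recalculation, reconcile Section 5 with Section 24 on whether the test question follows only from reported symptoms.

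The cost is a few sentences and one small table or tabulation. The downside is a less favourable stated detectable difference.

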V1.3	10/11/2023	Updated sections 6, 18, 19, 20 to clarify social media study participant engagement, data upload, analysis and anonymization processes, storage and protections.
V1.4	1/19/2023	Section 14, Recruitment Methods has been updated to describe new screening of potential participants to limit fraudulent enrollment.
V1.5	3/25/2024	Section 26 has been updated to clarify that Grady Health System / Grady Diabetes Clinic is a location for study promotion via flyers and palm cards.
V1.5	3/25/2024	Section 14, #3 has been updated to include addition of a text message check (receive and respond) during the eligibility interview to ensure a valid text message.
V1.6	4/26/2024	Section 14, Recruitment, has been updated to include the use of lists of participants from other RADxUP studies who agreed to be contacted about other studies they might be interested in.

Table of Contents

1. Study Summary	4
2. Objectives.....	5
3. Background	5
4. Study Endpoints	6
5. Study Intervention/Design	7
6. Procedures Involved.....	9
7. Data Specimen Banking.....	10
8. Sharing of Results with Participants.....	10
9. Study Timelines	10
10. Inclusion and Exclusion Criteria.....	10
11. Population	10
12. Vulnerable Populations	10
13. Local Number of Participants	10
14. Recruitment Methods	11
15. Risk to Participants.....	11
16. Potential Benefits to Participants.....	12
17. Compensation to Participants.....	12
18. Data Analysis, Management and Confidentiality	12
19. Provisions to Monitor the Data to Ensure the Safety of Participants	14
20. Provisions to Protect the Privacy Interest of Participants.....	14
21. Economic Burden to Participants	15
22. Informed Consent	15
23. HIPAA	16
24. Setting	16
25. Resources Available.....	17
26. Multi-Site Research When Emory is the Lead Site	18
27. References.....	19
28. Protocol Checklist.....	20

1. Study Summary

Study Title	PEACH ² : Promoting Engagement and COVID-19 Testing for Health
Study Design	A mixed methods community-based, adaptive intervention trial with quantitative and qualitative evaluation components.
Primary Objective	Understand the feasibility, acceptability and sustainability of COVID-19 home testing for high-risk individuals affected by or at risk for diabetes and their household contacts.
Secondary Objective(s)	Test the applicability of a text-based COVID-19 test result reporting system and targeted behavioral nudges for disease prevention in a pandemic situation

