23. HIPAA

This study will not record identifiers from medical records of living or non-living subjects. A unique study identifier will be created when the participant completes the informed consent and enrolls in the study. PHI collected is self-reported data and will be used to assign the participant to a nudge group based on how they are affected by or at risk for diabetes. Identifiable study data will be maintained in the study's secure REDCap project database, which is password protected and HIPAA compliant and in Georgia Tech's Nudge Platform. Only authenticated study team members that have assigned user privileges will have access to PHI.

24. Setting

Potential participants will be recruited through existing EU, MSM and GT partnerships with community based (RX MTM) and faith-based organizations (Big Miller Grove Baptist Church, Elizabeth Baptist Church), Diabetes clinics (Grady Diabetes Center) and FQHCs that serve communities at risk across Georgia. Partners will promote the study at their sites via in-person presentations, flyers and distribution of palm cards, or to their patients (clients), and direct them to the study website to complete the e-informed consent and online eligibility and study enrollment forms. Those that enroll will agree and consent to utilize their own cellular devices

to receive behavioral nudge text messages and submit responses about whether they had COVID symptoms in the past 30 days (Y/N) and if they took a COVID-19 test (Y/N).

The study will continue the community advisory board (CAB) started during Project PEACH, which is comprised of members of the partner organizations, community investigators, and local stakeholders. Partner organizations involved in Project PEACH, but not PEACH2, will be informed that they can choose to continue in an advisory role or leave the group as they wish. Any new community organizations that join the study team will have a member seated on the CAB. Members of partner organizations will not be involved in recruitment beyond the distribution of promotional information. Their participant-related contact will be limited to assisting participants to access the e-informed consent form.

25. Resources Available

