Facilities: Emory University (EU), Georgia Institute of Technology (GT) and Morehouse School of Medicine (MSM) all house institutes and centers that engage with or include the other partner institutions. The PEACH² study PIs and team members are members of the **Georgia Center for Diabetes Translation Research (GCDTR)** with PIs (EU: [name], [name] MSM: [name]; GT: [name]) also serving on or leading the GCDTR Cores (Design and Evaluation; Engagement and Behavior Change; Disparities; Enrichment Program). GCDTR Cores afford access to subject area expertise relevant to the study, including diabetes and related risk factor epidemiology, biostatistics, engineering, and demography. Other EU, GT, MSM collaborations and centers provide a rich pool of subject matter expertise and community partners that can be leveraged for this project. The Georgia Institute of Technology team members are also members of the **GT Institute for People and Technology** and **GT Center for Health and Humanitarian Systems**. The MSM team members are PIs and key investigators of the **Georgia CEAL**, the **GCTSA Community Engagement (CE) Program** and the **MSM Prevention Research Center (PRC)**. Further, each institution is involved in other RADx projects, such as The Atlanta Center for Microsystems Engineered Point-of-Care Technologies (ACME POCT)'s Rapid Acceleration of Diagnostics (RADx) Validation Core (U54 EB027690-02S1) at EU, Children's Healthcare of Atlanta. GT assesses user needs for novel COVID-19 devices and evaluates point of care devices for performance (EU/GT).

Study Team: PEACH2 PIs and study team members began collaborating during Project PEACH and will utilize lessons learned and gaps identified through Project PEACH as well as leverage community partnerships and infrastructure for this study.

Sample Size: The sample size of 600 was estimated using the following assumptions: (a) 80% power; (b) Alpha of 0.05; and (c) the percentage of participants receiving a COVID-19 test in the past month in the control arm would be equal to the percentage of the Georgia population getting a PCR test for COVID-19 in the month of June: 3.44 (standard deviation [SD] 0.49). Using these assumptions, a sample size of 520 (260 per study arm) will be powered to see an 4.5%

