increase in the percentage of individuals receiving COVID-19 in the intervention arm compared to controls. We plan to randomize 600 individuals to allow for attrition. In addition, given the rapidly changing status of COVID testing, we will employ a two-stage adaptive approach to recalculate sample size using first stage study data, as recommended by Brown and others for adaptive intervention studies.¹³

Medical or psychological resources: It is unlikely that study participants will require mental health support following participation in the study. Regardless, the study team will have a list of resources gathered from community partners to provide participants requesting help finding resources. There are no funds available to cover these services.

Research Team Preparation: The protocol and research procedures will be presented to study team members at partner institutions and organizations as they join the study team. SOPs that detail each activity (participant enrollment; survey data collection; qualitative data collection) will be reviewed with and available for the study team to follow. The study team will be organized into functional teams with scopes of work detailing functions for each role. Project coordinators will be responsible for ensuring team members on their teams are trained and understand the process, and for monitoring their work.

26. Multi-Site Research When Emory is the Lead Site

The total number of participants that will be recruited across the study is 600.

Study-wide Recruitment Methods/Participant Recruitment

Study partners (EU, GT, MSM) will utilize the same study recruitment methods as described in Section 14. All study partners will have access to copies of the most recent version of the protocol and study documents in SharePoint. Informed consent documents are available both in SharePoint and in REDCap at Emory. Relevant study team members (i.e., internal study team members; External Study Team List members whose roles include data collection) that will assist participants or conduct informed consent will have access to the most current documents in REDCap. All study team members involved in participant recruitment, performing informed consent, survey data collection and management, will undergo training.

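### The stated 80% power does not follow from the stated inputs: 260 per arm gives about 60% (two-sided) or 72% (one-sided) for 3.44% versus 7.94%

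*Combined protocol and SAP*

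**What the plan says.** Section 13 (Local Number of Participants) lists the assumptions as "a) 80% power; (b) Alpha of 0.05", plus a control-arm rate of testing in the past month set equal to "the percentage of the Georgia population getting a PCR test for COVID-19 in the month of June: 3.44 (standard deviation [SD] 0.49"). From these it concludes that "a sample size of 520 (260 per study arm) will be powered to see a 4.5% increase in the percentage of individuals" tested in the intervention arm compared with control. It then raises the number randomized to 600 to cover attrition.

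The Sample Size paragraph of Section 25 (Resources Available) repeats the calculation ("a sample size of 520 (260 per study arm) will be powered to see an 4.5"%) and adds that "we will employ a two-stage adaptive approach to recalculate sample size using first stage study data". No rule or formula is given for that step.

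Neither section names the test, says whether alpha is one- or two-sided, says whether 4.5% is in percentage points or relative, or explains what the 0.49 is the standard deviation of.

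**The concern.** The powered quantity is a percentage of individuals who were tested, so each participant contributes a yes or a no. For such an outcome, two rates, an alpha and a sample size fix the power of a simple comparison between arms. Control rates near 3% and an intervention rate near 8% looked too close together for 260 per arm to give 80%.

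The quoted SD added to the doubt. A yes/no outcome at 3.44% has a participant-level SD of about 18 percentage points, so 0.49 cannot be that quantity, and a two-proportion calculation needs no separate SD.

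What is at stake is how the nudge comparison will be read. A reader who trusts the printed 80% would take a non-significant result as fairly good evidence against a 4.5-point effect. At about 60% power that inference is much weaker.

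**Working it through.** **Inputs** (Sections 13 and 25): control rate p1 = 0.0344; increase 4.5%; alpha 0.05; target power 80%; 260 per arm, 1:1. Sidedness is not stated, so both are shown. Normal quantiles: 1.960 (two-sided), 1.645 (one-sided), 0.842 (80% power).

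**Step 1. Percentage-point reading, p2 = 0.0344 + 0.045 = 0.0794.**

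Mean rate = (0.0344 + 0.0794)/2 = 0.0569.
Variances: p1(1−p1) = 0.03322; p2(1−p2) = 0.07310; sum 0.10631. Pooled: 2 × 0.0569 × 0.9431 = 0.10732.

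Sample size per arm for 80% power, n = [z_alpha × √0.10732 + 0.842 × √0.10631]² / 0.045²:
- two-sided: (0.6421 + 0.2744)² / 0.002025 = 414.8, so 415
- one-sided: (0.5389 + 0.2744)² / 0.002025 = 326.6, so 327

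Power at 260 per arm, Φ[(0.045 − z_alpha × SE0)/SE1], with SE0 = √(0.10732/260) = 0.02032 and SE1 = √(0.10631/260) = 0.02022:
- two-sided: (0.045 − 0.03982)/0.02022 = 0.256, power 60.1%
- one-sided: (0.045 − 0.03342)/0.02022 = 0.573, power 71.7%

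**Step 2. Does the choice of test matter?** Power at 260 per arm:

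| Method | Two-sided | One-sided |
|---|---|---|
| Pooled z | 60.1% | 71.7% |
| Unpooled z | 60.5% | 71.9% |
| Arcsine | 61.8% | 73.1% |
| Exact power of the pooled z (chi-square) test | 61.0% | 73.0% |
| Exact power of Fisher's test | 54.5% | 67.0% |

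With all 300 per arm analysed, the pooled formula gives 66.3% and 77.0%. Moving the control rate by 0.49 points either way (2.95% to 3.93%) gives 63.8% to 56.8% two-sided at 260.

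**Step 3. Other readings of 4.5% and of the SD (two-sided).**

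| Reading | Result |
|---|---|
| Relative rise, 3.44% to 3.44 × 1.045 = 3.59% | about 222,000 per arm for 80% |
| Rise to 4.5% | about 5,300 per arm for 80%; power 9.0% at 260 |
| Means, SD 0.49, difference 3.44 × 0.045 = 0.1548 | 95.0% power at 260; about 158 per arm for 80% |

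For the last row, the standard error is 0.49 × √(2/260) = 0.04298, and 0.1548/0.04298 − 1.960 = 1.642, which gives 95.0%. On that route 260 per arm detects 0.120 with 80% power, which is 3.5% of 3.44, not 4.5%. The participant-level SD of a yes/no outcome at 3.44% is √0.03322 = 0.182, or 18.2 percentage points.

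**Step 4. The closest route to 260.** Applying the control-arm variance to both arms, two-sided, gives 2 × 0.03322 × (1.960 + 0.842)² / 0.002025 = 257.5, so 258 per arm, and a nominal 80.4% at 260. This is near the printed figure, but it ignores the variance at 7.94%, which is more than twice as large (0.0731 against 0.0332). The documents do not say that this was the method.

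**Step 5. What 260 per arm can detect with 80% power** (pooled formula, solved for p2): 6.0 points two-sided (to about 9.5%) or 5.2 points one-sided. At 300 per arm: 5.5 and 4.7 points.

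**The case against.** The strongest reply is that the original calculation can nearly be recovered. The control-variance route in step 4 lands on 258 per arm, which suggests a two-sided calculation in percentage points with one specific shortcut. On that view the much larger sample sizes under the relative and rise-to-4.5% readings are unlikely to reflect what was intended. That is fair as a guess at the cause, and the percentage-point reading is the one to work with. It does not rescue the 80%, because the shortcut is itself the error.

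Second, the analysis is not specified. Section 5 surveys everyone at months 4 and 12, and an analysis using both would be more efficient. As an illustration only, averaging two measurements with an assumed within-person correlation of 0.1 to 0.5 would give about 85% down to 73% two-sided power at 260. No such analysis is described, and the stated outcome is testing in the past month, so this does not support the printed sentence. It does mean that the 40% miss rate holds only for a single unadjusted comparison.

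Third, the text-message item in Section 24 ("about whether they had COVID symptoms in the past 30 days (Y/N) and if they took a COVID-19 test (Y/N") is weak evidence about the powered outcome, since Section 5 asks about testing only after symptoms are reported. That stands, but it is not needed: a percentage of individuals tested is a yes/no outcome by itself.

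Finally, the stakes are modest. The primary objective in Section 1 is "Understand the feasibility, acceptability and sustainability of COVID-19 home testing for high-risk individuals" and their household contacts; the nudge test is secondary, and the sample size is open to recalculation. This limits the severity and does not make the figure right.

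**Conclusion.** The concern holds. Sections 13 and 25 print 80% power for 260 per arm, and no valid reading of their inputs that was tried yields it. On the most favourable two-proportion reading, 3.44% versus 7.94%, power is about 60% two-sided or 72% one-sided. The stated 260 per arm compares with 415 or 327 needed. If 260 per arm were the final analysed number, a two-sided test would miss a true 4.5-point increase about 40% of the time rather than 20%.

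This rests on a single unadjusted comparison of proportions between two equal arms at alpha 0.05, and on taking 4.5% as percentage points, which the text does not say. It should be fixed, but it does not threaten the primary objective. Where the 260 came from remains unknown.

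**What to change.** Retrieve the original calculation, then amend Sections 13 and 25 in the same way:

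1. State the test, whether it is one- or two-sided, and whether 4.5% means percentage points or a relative increase.
2. Say what the SD of 0.49 describes and how it was used, or delete it.
3. Replace the power statement with one that follows from the inputs. If two-sided in percentage points: *With 260 analysed per arm, power for a 4.5-point increase from 3.44% is about 60%; 80% power is reached for an increase of about 6.0 points (to about 9.5%).* If one-sided, the figures are 72% and 5.2 points. Present this as the detectable difference, not as a new target.

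The cost is wording in two places and a less favourable printed figure. These three items need no additional enrolment.

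Optionally, name the formula for the recalculation in Section 25, so that it allows for the larger variance at the assumed intervention rate. It can be run on the blinded overall rate plus the assumed difference: 5.69% overall with 4.5 points returns 415 per arm, the same as step 1. On the current assumptions that is 830 analysed against 600 planned, so the section should also say what happens if the recalculated number exceeds what can be enrolled. The correction in items 1 to 3 does not depend on this.
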